3.2.5. Rationale for Selection of 2q3wk LV Dose (Part C)

LV monotherapy has been extensively evaluated across a range of doses and schedules in subjects with mBC in the concurrently ongoing phase 1 study SGNLVA-001 (see Section 1.2.4.3). In Part E of this study, 81 patients with mBC received LV administered at 1.0, 1.25, or 1.5 mg/kg weekly (q1wk). No DLTs were observed at any of the 3 starting doses evaluated in the dose escalation phase (Seagen Inc., data on file).

Preliminary efficacy results from Part E of the SGNLVA-001 study are shown in Figure 1 in Section 1.2.4.4 (data cut 06-Jan-2021). There appears to be greater magnitude of tumor size reduction with increasing dose of LV q1wk with the 1.5 mg/kg dose having the highest proportion of patients with measurable response. However, the frequency of AEs generally appears to increase with increasing dose as well. Table 2 in Section 1.2.4.3 summarizes the most commonly reported AEs by dose in SGNLVA-001 (26-July-2021, Seagen Inc., data on file). Due to the high frequency of neutropenia at the LV 1.5 mg/kg q1wk dose, (67% of patients with 44% of patients having Grade ≥ 3), accrual to this expansion cohort was paused. Although higher efficacy had been observed with the 1.5 mg/kg dose level, the better safety and tolerability of the 1.25 mg/kg dose led to further expansion of this cohort.

In the patients treated with LV monotherapy at the 1.25 mg/kg q1wk dose level, the relative dose intensity started to decrease by Cycle 2 (C2) leading to 2 doses being administered in every 3-week cycle. Similarly, most of the clinically significant neutropenia events in the 1.5 mg/kg dose level occurred after 3 weekly doses. Overall, these observations suggested that an LV drug holiday may be needed to mitigate AEs, including neutropenia, for long-term treatment. This is further supported by PK simulation which demonstrated that giving LV 1.5 mg/kg on Days 1 and 8 every 21 days (2q3wk) would result in similar PK exposures as 1.25 mg/kg q1wk dosing schedule. Based on this rationale, the intermittent dosing schedule of LV 1.5 mg/kg 2q3wk is being explored as monotherapy in Part F of study SGNLVA-001.

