5.2.4.2. Part B (q1wk dosing) and Part C (Arm 3; q1wk dosing)

In the event of an AE or lab criteria that prevents dosing of LV (see Section 5.2.3.1), the LV dose for the week should be withheld. LV may be resumed when the dosing criteria are met. If a dose(s) of LV is withheld, the corresponding visit may be skipped and resume the following week (eg, if the Day 8 dose is skipped, visits will resume on Day 15; if Day 8 and Day 15 doses are skipped, visits will resume on Day 1 of the following cycle). Day 1 of a cycle may be delayed but not skipped.

Dose reduction of LV may be considered in the event of recurrent AE despite withheld doses. Dose re-escalation following dose reduction is not allowed. Dose levels for LV dose reductions in Part B and Part C (Arm 3) are shown in [Table 11](#).

For Part C (Arm 3), subjects who discontinue pembrolizumab due to a pembrolizumab-related AE (see Section 5.3.4) may continue LV. Similarly, subjects who discontinue LV for a LV-related AE may continue pembrolizumab. See Section 5.5.3 for details on managing overlapping AEs.

Table 11: Q1wk LV dose reductions

Starting Dose	First Dose Reduction (mg/kg/wk)	Second Dose Reduction (mg/kg/wk)
Starting dose 1.0 mg/kg/wk	0.75	0.5
Starting dose 1.25 mg/kg/wk	1.0	0.75

For nonclinical events requiring alteration in dosing schedule (eg, holidays, scheduling conflicts), a +2 day dosing window is allowed. Nonclinical events that require skipping a dose(s), must be approved by sponsor medical monitor. At least 7 days must elapse between each administration of LV.

Dose modification guidelines for LV q1wk treatment-associated toxicity are detailed in [Table 12](#).

Table 12: Dose modifications for LV treatment-associated toxicity (Part B and Part C [Arm 3] q1wk dosing)

Toxicity	Grade 1	Grade 2	Grade 3	Grade 4
Peripheral neuropathy ^a	Continue at same dose level	Withhold until toxicity resolves to \leq Grade 1; treatment may resume at the next lower dose level (see Table 11)	Withhold until toxicity resolves to \leq Grade 1, then resume treatment at the next lower dose level (see Table 11)	Discontinue treatment
Hyperglycemia		Hold for blood glucose >250 mg/dL or >13.9 mmol/L. Resume treatment once elevated blood glucose has improved to ≤ 250 mg/dL or ≤ 13.9 mmol/L and subject is clinically and metabolically stable (see Section 5.6 for details).		

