5.2.4.3. Part C (Arm 1 and Arm 2; 2q3wk dosing)

In the event of an AE or lab criterion that prevents dosing of LV (see Section 7.6.1), the LV dose should be withheld until the dosing criteria are met. If the Day 1 dose is held, the Day 8 dose should not be given until 7 days later.

In the event of an AE or lab criterion that prevents dosing of LV on Day 8 during the cycle (see Section 7.6.1), the LV dose for the week may be withheld up to 4 days for Arm 1 and Arm 2. LV may be resumed when the dosing criteria are met. If a dose of LV is withheld for more than 4 days, the corresponding visit may be skipped and dosing resumed at the following visit (eg, if the Day 8 dose is skipped, visits will resume on Day 1 of the following cycle). Day 1 of a cycle may be delayed but not skipped.

Dose reduction of LV may be considered in the event of recurrent AE despite withheld doses. Dose re-escalation following dose reduction is not allowed. Dose levels for LV dose reductions in Part C (Arms 1 and 2) are shown in [Table 13](#) .

For Arm 2, subjects who discontinue pembrolizumab due to a pembrolizumab-related AE (see Section 5.3.4) may continue LV. Similarly, subjects who discontinue LV for a LV-related AE may continue pembrolizumab. See Section 5.5.3 for details on managing overlapping AEs.

Dose modification guidelines for LV 2q3wk treatment-associated toxicity are described in [Table 13](#) (Arm 1 and Arm 2).

Table 13: 2q3wk LV dose levels

Starting dose	First dose reduction	Second dose reduction ^a
1.5 mg/kg	1.25 mg/kg	1.0 mg/kg ^b

^a If patients have more than 2 dose reductions (with medical monitor approval), dose will be the next appropriate reduced dose level determined by discussion between investigator and medical monitor.

^b The dose may be reduced to 0.75 mg/kg following approval from the medical monitor.

For nonclinical events requiring alteration in dosing schedule (eg, holidays, scheduling conflicts), a +4-day dosing window is allowed. If more than a +4-day window is needed, the medical monitor must be consulted. The medical monitor must approve skipped dose(s) for nonclinical events. At least 7 days must elapse between administrations of LV.

[Table 14](#) describes dose modifications for LV treatment-associated toxicity for the 2q3wk schedule (Arm 1 and Arm 2).

Doses reduced for LV-related toxicity should not be re-escalated.

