6.4.3.4. Day 15 (\pm 2 days)

Note: Subjects in Arm 1 and Arm 2 will require the following:

- CBC with differential (–2-day window; see Section 7.6.3; results to be submitted to iRIS), Cycles 1 and 2 only
- Physical exam (C1 only; see Section 7.6.4)

The following is for Arm 3 only:

Predose

- Confirm subject meets dosing criteria (Section 5.2.3.1)
- Physical exam (C1 only; see Section 7.6.4)
- CBC with differential (see Section 7.6.3; results to be submitted to iRIS), Cycles 1 and 2 only
- Serum chemistry panel and liver function tests (see Section 7.6.3; results to be submitted to iRIS), Cycles 1 and 2 only
- Random blood glucose in Cycles 1 and 2. Following C2, random blood glucose may be collected as indicated in subjects at risk for hyperglycemia. (see Section 5.6; results to be submitted to iRIS)
- Vital signs (within 60 minutes prior to the start of LV infusion, see Section 7.6.2)
- Blood samples for PK assessment (C1 and C4 only; see Section 7.3 for time points)
- Blood samples for biomarker assessment (C1 and C2 only; see Section 7.4.1)
- LV administration (a +2 day dosing window is allowed for subsequent dosing within a cycle; see Sections 5.2.3 and Section 5.2.4.2). For nonclinical events requiring skipping a dose(s), must consult with and obtain approval by sponsor medical monitor. At least 7 days must elapse between administrations of LV.

Postdose

- Vital signs (within 2 hours of ending each infusion, and during infusion(s) as clinically indicated; see Section 7.6.2)
- Blood samples for PK assessment (C1 and C4 only; see Section 7.3 for time points)

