APPENDIX D. SCHEDULE OF EVENTS FOR TREATMENT (PART C)

Arms 1 and 2 (2q3wk dosing)

	Assessment	Enrollment	Cycle 1				Cycle 2+				EOT	F/U
	Day	Within 7D of 1st dose	D1	D3	D8	D15	D1	D3	D8	D15	Within 30–37D of last dose ^a	Every 6 or 12 weeks
	Visit window		0d ^b	+ 1d	+ 4d	– 2d	+ 4d	+ 1d	+ 4d	– 2d		± 3d or ± 7d
	Confirm subject meets dosing criteria		X		X		X		X			
Treatment	LV administration		X		X ^c		X ^c		X ^c			
	Pembrolizumab administration (Arm 2)		X				X					
Safety Assessments	Pregnancy test (females of childbearing potential only)	Submit eligibility confirmation to sponsor prior to treatment	X ^d				X				X	X ^e
	HbA1c										X	
	Physical exam		X ^d		X	X	X				X	X ^f
	Weight		X ^d				X				X	
	CBC with differential		X ^d		X ^g	X ^g	X		X ^g	X ^g	X	
	Chemistry panel and liver function tests		X ^d		X ^g		X		X ^g		X	
	Random blood glucose ^h		X		X		X					
	Thyroid function tests (Arm 2) ⁱ		On Day 1 of each odd-numbered cycle while on treatment (eg, Cycles 1, 3, 5, etc)									
	Vital signs ^j		X		X		X		X		X	
	ECOG performance status		X ^d				X				X	

	Assessment	Enrollment	Cycle 1				Cycle 2+				EOT	F/U
	Day	Within 7D of 1st dose	D1	D3	D8	D15	D1	D3	D8	D15	Within 30–37D of last dose ^a	Every 6 or 12 weeks
	Visit window		0d ^b	+ 1d	+ 4d	– 2d	+ 4d	+ 1d	+ 4d	– 2d		± 3d or ± 7d
	Concomitant medications	Related to study procedures	Arm 1: Collect from Day 1 predose to EOT or 30 days post last dose, whichever is later Arm 2: Collect from Day 1 predose to EOT or 90 days post last dose, whichever is later									
	AE collection											
Biomarker Assessments	Blood samples for biomarker assessment (see Section 7.4.1)		See Table 19									
	Tumor biopsy for research (see Section 7.4.2)											
PK/ATA	Samples for PK testing (see Section 7.3)		See Table 19									
	Samples for ATA testing (see Section 7.3)											
Response Assessments	CT/MRI ^k		Every 6 weeks (± 3 days) for the first 12 months, then every 12 weeks (± 7 days) thereafter ^l								X ^m	X ^f
	Survival follow-up contact											

2q3wk=dosing on Day 1 and Day 8 but not Day 15 of each 21-day cycle; D=day; F/U=follow-up

^a EOT evaluations should be obtained before the initiation of non protocol therapy. If EOT evaluations are completed before 30 days following the last study treatment, conduct a phone screen 30–37 days following the subject's last study treatment to ensure that no changes in AE profile have occurred.

^b Visit window does not apply to C1, Day 1.

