^c A +4 day dosing window is allowed. At least 7 days must elapse between administrations of LV.

^d Not required in Cycle 1 if baseline was assessed within 3 days prior to first dose of study drug.

^e Only tested once at 24 weeks after last dose of LV

^f Every 6 weeks (± 3 days) for the first 12 months after the first dose of LV, then every 12 weeks (± 7 days) thereafter. Continue to assess until disease progression. After a year of follow up, reducing scanning frequency to institutional standard of care

^g Only required for Cycle 1 and Cycle 2.

^h Random blood glucose should be checked prior to dosing on each dosing day of the first 2 cycles. For Cycle 3 and later, blood glucose should be checked on Day 1 of each cycle and may be checked on Day 8 if clinically indicated, particularly in subjects at risk for hyperglycemia (Section 5.6).

ⁱ Thyroid function tests include TSH, T3 or free T3, and free T4

^j Arm 1: Vital signs to be within 60 minutes prior to the start of LV infusion, within 30 minutes after completion of LV infusion, and during infusion as clinically indicated.

Arm 2: Vital signs to be within 60 minutes prior to the start of LV infusion, within 60 minutes prior to pembrolizumab infusion (Day 1 only), within 2 hours of ending each infusion, and during infusion(s) as clinically indicated.

^k See Section 7.2.1 for tumor cohort specific imaging requirements. Submit copies of images to independent review facility.

^l If required, it is recommended that scans not be scheduled on the dosing day. It is recommended that scans done on the same day as Day 1 of subsequent cycles be completed and reviewed prior to infusion with LV.

^m Not required if conducted within 4 weeks prior to EOT.

Arm 3 (q1wk dosing)

	Assessment	Enrollment	Cycle 1				Cycle 2+				EOT	F/U
	Day	Within 7D of 1st dose	D1	D3	D8	D15	D1	D3	D8	D15	Within 30–37D of last dose ^a	Every 6 or 12 weeks
	Visit window		+ 2d ^b	+ 1d	+ 2d	+ 2d	+ 2d	+ 1d	+ 2d	+ 2d		± 3d or ± 7d
	Confirm subject meets dosing criteria			X		X	X	X		X	X	
Treatment	LV administration		X		X ^c	X ^c	X ^c		X ^c	X ^c		
	Pembrolizumab administration		X				X					
Safety Assessments	Pregnancy test (females of childbearing potential only)	Submit eligibility confirmation to sponsor prior to treatment	X ^d				X				X	X ^e
	HbA1c										X	
	Physical exam		X ^d		X	X	X				X	X ^f
	Weight		X ^d				X				X	
	CBC with differential		X ^d		X ^g	X ^g	X		X ^g	X ^g	X	

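### Part C Arms 1 and 2, Cycles 1–2: the example in Protocol 5.2.4.3 for a skipped Day 8 dose, read literally, drops the Day 15 blood count and the Cycle 1 examination that 6.4.3.4 and Appendix D require (minor)

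*Protocol*

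**What the plan says.** **Dose-modification text.** Protocol 5.2.4.3 covers the 2q3wk schedule of Arms 1 and 2. When an adverse event or laboratory criterion prevents the Day 8 dose, "the LV dose for the week may be withheld up to 4 days for Arm 1 and Arm 2". It continues: "If a dose of LV is withheld for more than 4 days, the corresponding visit may be skipped", with dosing then taken up at the next visit. The example in parentheses reads "if the Day 8 dose is skipped, visits will resume on Day 1 of the following cycle".

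**Visit text.** Protocol 6.4.3.4 (Day 15) opens with "Note: Subjects in Arm 1 and Arm 2 will require the following" and lists two items: a CBC with differential in Cycles 1 and 2 (window −2 days) and a physical examination in Cycle 1. Neither depends on what happened on Day 8.

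**Schedule.** The Appendix D table for Arms 1 and 2 has a Day 15 column marking the same two items. The footnote to the Day 8 and Day 15 CBC says "Only required for Cycle 1 and Cycle 2". No LV dose is marked on Day 15 in these arms.

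**The concern.** Two parts of the protocol give a site different instructions for the same subject. One sends the subject from a skipped Day 8 straight to the next cycle's Day 1. The other expects the subject on Day 15 for a count and, in Cycle 1, an examination. Because Day 15 is not a dosing day in these arms, a held dose is no reason to drop it.

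The affected subjects are those already showing a toxicity or failing a laboratory criterion. Neutropenia is part of the rationale for the schedule: Protocol 3.2.5 says that "an LV drug holiday may be needed to mitigate AEs, including neutropenia, for long-term treatment". Table 14 also ties growth-factor support in later cycles to the grade of neutropenia reached, so an omitted count could leave a worse grade unseen. Sites following different sections would monitor the same situation differently, and each could be cited for deviating from the other section.

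**Working it through.** The plan states no figure to reproduce. The check has two parts: the texts side by side, and the intervals between counts.

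**Texts, for an Arm 1 or 2 subject whose Day 8 dose is skipped**

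| Cycle | 5.2.4.3 example, read literally | 6.4.3.4 and Appendix D | Conflict |
|---|---|---|---|
| 1 | Next visit is Cycle 2 Day 1 | Day 15 CBC and physical examination | Both items |
| 2 | Next visit is Cycle 3 Day 1 | Day 15 CBC | CBC only |
| 3 onward | Next visit is next-cycle Day 1 | No Day 15 CBC or examination | None |

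Protocol 6.1 says where the schedules and visit lists are found. It does not say which section prevails when they disagree.

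**Intervals between counts, Cycles 1–2**

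Inputs: a 21-day cycle, so the next Day 1 falls on Day 22; required counts on Days 1, 8 and 15 (6.4.3 and Appendix D); a permitted hold of 4 days (5.2.4.3). Visit windows and any delay of Day 1 are ignored.

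- As scheduled: 8 − 1 = 15 − 8 = 22 − 15 = 7 days.
- Day 15 omitted, count drawn on Day 8: 22 − 8 = 14 days.
- Day 15 omitted, recheck on the last permitted hold day, 8 + 4 = Day 12: 22 − 12 = 10 days.

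The typical gap is therefore 10 to 14 days, against 7 as scheduled.

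**Fit with the existing window.** The first day beyond the 4-day hold is Day 13. The Day 15 CBC window runs from 15 − 2 = Day 13 to Day 15. One draw can serve both as follow-up of the hold and as the required count.

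**Subjects under this text.** 30 + 30 = 60 planned in Arms 1 and 2. Only those whose Day 8 dose in Cycle 1 or 2 is withheld for more than 4 days are concerned, and the documents give no rate for that.

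**The case against.** The strongest reply is that the example was meant for dosing visits only. It sits in a dose-modification section, its main clause speaks of resuming dosing, and the permission to skip covers only the Day 8 visit. In these arms the next visit at which LV can be given is indeed Day 1. The parallel weekly rule in 5.2.4.2 also speaks of visits resuming on Day 15, but that is a dosing day there, so it does not settle the meaning. An unconditional requirement in the assessment section should also carry more weight than an example attached to an optional skip. This reading is plausible and may be what was intended, but the example says *visits* and nothing limits the word.

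The safeguards are real and keep the consequence small:

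- Protocol 5.2.3.1 requires neutrophils of at least 1000/µL before any Day 1 or Day 8 dose.
- Table 14 holds Grade 3–4 hematologic toxicity until recovery to Grade 2 or baseline, and requires growth-factor treatment for febrile neutropenia.
- An abnormality that interrupts dosing is an adverse event with recorded onset and resolution dates (7.6.1.1, 7.6.1.2).
- From Cycle 3 the plan schedules no Day 15 count even after a full Day 8 dose, so it accepts a 14-day gap later on.

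None of these restores the Day 15 count in the two cycles where the plan chose closer monitoring.

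Two stronger readings are tempting. A reader might infer that counts could be a full cycle apart. That needs no draw at all after Day 1, whereas a Day 8 CBC is itself required in Cycles 1 and 2 (6.4.3.3), so it is an edge case. A reader might also see the same contradiction for Part B and Arm 3, where 5.2.4.2 says "If a dose(s) of LV is withheld, the corresponding visit may be skipped and resume the following week". There the visit belongs to the withheld dose and the permission to skip it is deliberate. It contradicts nothing and needs no added sentence.

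**Conclusion.** The inconsistency stands, and it is minor. In Cycles 1 and 2 of Arms 1 and 2, the example in 5.2.4.3 taken at its word conflicts with the Day 15 CBC and the Cycle 1 Day 15 examination. Each such hold would lose one required count and, in Cycle 1, one examination, leaving typically 10 to 14 days between counts instead of 7. This assumes that the site uses the optional skip and follows the example literally, that a count was drawn on Day 8 or by Day 12, and that Day 1 is not delayed.

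A reader might infer that held subjects could be redosed without a count. Protocol 5.2.3.1 rules that out. A reader might also infer that the safety tables would be materially understated. A missing count can only leave a subject's worst grade unchanged or lower, but with no rate of skipped Day 8 doses no size can be given. The neutropenia rates in 3.2.5 for 1.5 mg/kg weekly cannot supply one, because most of the clinically significant events there followed three weekly doses. The objective response rate and the sample size are not touched.

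**What to change.** Reword the example in Protocol 5.2.4.3 along these lines: *if the Day 8 dose is skipped, dosing will resume on Day 1 of the following cycle; the Day 15 CBC (Cycles 1 and 2) and the Cycle 1 Day 15 physical exam are still done.* Dosing rules, 6.4.3.4 and Appendix D stay as they are, and 5.2.4.2 needs no change.

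The cost is one sentence. The assessments are already scheduled, and Protocol 7.6.3 already uses local laboratories. The downside is an occasional blood draw and, in Cycle 1, an examination in a week without an infusion.

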5.2.5. Storage and Handling

Single-use vials containing LV must be stored under refrigeration set at 2–8 °C in an appropriate locked room accessible only to the pharmacist, investigator, or a duly designated person.

Chemical and physical stability of the reconstituted drug product has been demonstrated for 24 hours at 2–8 °C and at room temperature. However, LV drug product does not contain preservatives; therefore, from a microbiological standpoint, opened and reconstituted vials should be used immediately. If not used immediately, the in-use storage should not be longer than 24 hours under refrigeration set at 2–8 °C. The prepared dosing solution (reconstituted drug product solution and saline dilution in an IV bag or polypropylene syringe) should be administered within 8 hours after exposing to ambient temperature and light conditions.

It is recommended that the drug product vials and solutions be protected from direct sunlight until the time of use.

Do not shake reconstituted LV.

Any partially used vials or prepared dosing solutions should be discarded by the site according to institutional drug disposal procedures. Unused vials may only be discarded by the site after authorization by the sponsor or designee.

Specific instructions for the preparation, handling, storage, and accountability are found in the Pharmacy Manual.

5.2.6. Packaging and Labeling

LV is supplied in single-use glass vials. The drug product vials are labeled as SGN-LIV1A, the compound code.

5.2.7. Preparation

Recommended safety measures for handling and preparation include masks, protective clothing, gloves, and vertical laminar airflow safety cabinets.

Before administration, LV must be reconstituted and diluted. Diluted solutions of LV are stable at a concentration range of 0.3 mg/mL to 2.5 mg/mL. The formulation contains no preservative and is intended for single use only; infusion solutions should be prepared and transferred using aseptic technique in a biosafety hood.

Mixing of lot/batch numbers is not allowed for preparation of a single dose; however, use of a different lot/batch number is allowed for subsequent doses during treatment cycles.

Detailed instructions for dose preparation are provided in the Pharmacy Instructions.

5.3. Pembrolizumab

Patients will receive pembrolizumab 200 mg in combination with LV.

5.3.1. Description

Pembrolizumab (MK-3475) will be supplied as a 100 mg/4 mL (25 mg/mL) solution in a single-use vial.

Pembrolizumab for injection is a sterile, preservative-free, clear to slightly opalescent, colorless to slightly yellow solution that requires dilution for IV infusion. Each vial contains 100 mg of pembrolizumab in 4 mL of solution. Each 1 mL of solution contains 25 mg of pembrolizumab and is formulated in L-histidine, polysorbate, sucrose, and WFI USP.

5.3.2. Method of Procurement

Pembrolizumab will be provided to all study sites by the sponsor. In countries outside the US, pembrolizumab will also be relabeled by the sponsor, to meet country-specific regulatory requirements.

